### **Procedures**

1. Patients who meet the criteria and agree to participate in the study taken as the subject of the research.
2. Research subjects were then randomized into two groups. The control group (Group A) and the treatment group (Group B) as the group that receiving intra aortic balloon pump (IABP) as early as possible within 3 hours after the return of spontaneous circulation (ROSC). IABP insertion is performed by an interventionist.
3. Baseline data such as age, weight, height, risk factor (hypertension, Diabetes Mellitus,

dyslipidemia, smoking, family history), history of Acute Myocardial Infarct (AMI), Percutaneous Coronary Intervention (PCI), Coronary Artery Bypass Graft (CABG), and valvular disease will be taken. Vital signs examination and EKG 12 leads will be performed.

- Laboratory tests for peripheral venous blood include: Lactate levels, urea (Ur), creatinine (Cr), n-terminal pro B-type natriuretic peptide (NT Pro BNP), high sensitive troponin (Hs Trop), IL-6, beclin 1 and caspase 3.
  - Central venous blood examination for central venous blood gas analysis includes assessment of a-vO2 diff and ScvO2.
  - Arterial blood examination for arterial blood gas analysis.  
Monitoring of hemodynamic parameters using echocardiography machines (ejection fraction, TAPSE, cardiac output, VTI).
4. In the group B, IABP is initiated within 3 hours after the return of spontaneous circulation by the interventionist.
  5. Blood sampling is repeated at 6th hour post ROSC or 1 hour post-insertion of IABP consisting of:
    - Laboratory tests for peripheral venous blood include lactate, IL-6, beclin-1 and caspase 3 levels.
    - Central venous blood examination for central venous blood gas analysis includes assessment of a-vO2 diff and ScvO2.
    - Arterial blood examination for arterial blood gas analysis.  
Examination of hemodynamic parameters with echocardiographic machine was repeated at the 6th hour post ROSC, consisting of ejection fraction, TAPSE, cardiac output, VTI).
  6. Research subjects will be monitored during hospitalization.

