### **Analysis Method**

Data analysis using SPSS 20.0 software program with appropriate statistical test. Data taken during the study will be displayed according to the variable type. Numerical variables with normal distribution will be displayed as mean  $\pm$  standard deviation, which is then analyzed by a general linear model (GLM) test for data measured more than once (IL-6, Beclin-1, Caspase-3, a- vO2 diff, and ScvO2) and independent t test for data with one time measurement (mortality rate in hospital and effective lactate clearance). Numerical variables with abnormal distribution will be shown in median (minimum-maximum) and then analyzed by Mann-Whitney test. The categorical variable will be displayed as a percentage (number) and will be analyzed by chi-square test or alternate test.

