### **Primary Outcome**

In-hospital mortality

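### The primary mortality comparison is unadjusted although age and a first lactate are already collected: valid under randomisation, but probably less precise than it could be

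*Combined protocol and SAP*

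**What the plan says.** The Primary Outcome section names "In-hospital mortality". The Analysis Method section lists it with the numerical variables measured once, for an "independent t test for data with one time measurement (mortality rate in hospital and effective lactate clearance". Its last sentence reads "The categorical variable will be displayed as a percentage (number) and will be analyzed by chi-square test or alternate test". Whichever line is applied to mortality, the comparison is between two groups with no covariates. The only model in the plan, a general linear model, is reserved for the repeatedly measured markers; mortality is not among them and no covariate is named for any analysis.

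Item 3 of Procedures collects "Baseline data such as age, weight, height, risk factor" and other history. Its blood tests are introduced by "Laboratory tests for peripheral venous blood include: Lactate levels, urea (Ur), creatinine (Cr" and further markers. Item 3 comes after randomisation (item 2) and before the start of the balloon pump in Group B (item 4). A second draw follows: "Blood sampling is repeated at 6th hour post ROSC or 1 hour post-insertion of IABP". Item 2 says that subjects are randomised into two groups and mentions no stratification factor.

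**The concern.** Patients may be of any age between 18 and 75, and all have just survived a cardiac arrest. Age and early lactate are plausible predictors of in-hospital death in such a group, though the documents do not quantify this. If they do predict death, an unadjusted comparison leaves explainable variation in the error term and its confidence interval is wider than necessary.

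The second issue is interpretation. If the arms differ visibly in age or lactate, the planned estimate does not account for it. An adjusted analysis chosen after the imbalance is seen is open to the charge that it was picked to suit the data. Naming the covariates in advance avoids that and needs no new measurements.

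**Working it through.** **Inputs.** From the documents: a binary primary outcome, two randomised groups, age and a first lactate collected. Not in the documents: sample size, alpha, power, mortality rates, allocation ratio and the prognostic strength of either covariate. There is therefore no planned figure to reproduce, and everything below is assumed: two-sided 5%, 1:1 allocation, and the rates and odds ratios stated.

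**Step 1: closed form.** If the covariates explain a share R² of the variance in death, the required n is multiplied by about (1 − R²). At 60% v 40% mortality and 80% power:

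n per arm = [1.96·√(2·0.5·0.5) + 0.842·√(0.6·0.4 + 0.4·0.6)]² / 0.2² = (1.386 + 0.583)² / 0.04 ≈ 96.9, so 97 per arm and 194 in total.

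| R² | Total N for 80% power | Power at N = 194 |
|---|---|---|
| 0 | 194 | 80% |
| 0.05 | 186 | 82% |
| 0.10 | 176 | 84% |
| 0.20 | 156 | 88% |

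This ignores the cost of estimating the covariate effects, which matters in small trials.

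**Step 2: simulation at 61% v 35% mortality.** Mortality has to be held fixed across settings; if a conditional odds ratio is fixed instead, the true risk difference changes with covariate strength and the power figures are not comparable. As a check, the unadjusted two-proportion test with 50 per arm has power Φ[(0.26 − 1.96·√(2·0.48·0.52/50)) / √((0.61·0.39 + 0.35·0.65)/50)] = Φ[(0.26 − 0.196)/0.0965] ≈ 74.7%.

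The simulation used 4000 replicates per setting and compared a pooled z test with a linear model with robust (HC3) standard errors:

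| Per arm | Odds ratio per SD, age / lactate | Power, unadjusted → adjusted | Variance ratio |
|---|---|---|---|
| 50 | 1.5 / 2.0 | 76.2% → 79.0% | 0.89 |
| 50 | 1.5 / 2.5 | 76.6% → 81.2% | 0.88 |
| 30 | 1.5 / 2.0 | 55.6% → 57.6% | 0.92 |
| 30 | 1.5 / 2.5 | 53.8% → 57.5% | 0.88 |
| 50 | 1.5 / 1.5 | about unchanged | 0.94 |

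Type I error of the adjusted test was 4.6% to 5.5%. With non-prognostic covariates, power fell by about 3 points. The Monte Carlo error of each power figure is about √(0.76·0.24/4000) = 0.7 points. Repeat runs at the same fixed rates put the variance reduction at 8-15% and the gain at 2-5 points for lactate odds ratios of 2.0-2.5.

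**Step 3: a smaller effect and smaller trials.** At 60% v 40%, with HC3 errors and a t reference, power without → with adjustment was:

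| Total N | R² about 0.10 | R² about 0.20 |
|---|---|---|
| 30 | 18% → 16% | 19% → 18% |
| 100 | 55% → 54% | 54% → 59% |
| 200 | 83% → 85% | 83% → 89% |

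The variance gain at R² about 0.10 (relative efficiency 1.02 at N = 30, about 1.09-1.10 at N = 100-200) becomes power only in the larger trial.

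**Step 4: validity and imbalance.** With no treatment effect, the unadjusted test rejected in 4.2% to 5.9% of runs. The standardised mean difference of a covariate has SD 2/√N, so the chance that at least one of two independent covariates differs by more than 0.25 SD is 1 − [1 − 2·(1 − Φ(0.25·√N/2))]². That is 56% at N = 60, 38% at N = 100 and 15% at N = 200.

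**The case against.** The strongest reply is that this is a preference about efficiency. Randomisation and the error rate of the test already allow for chance imbalance, and Step 4 bears that out. This stands. A reader might infer that the planned comparison is biased, or that nothing protects it against imbalance; the documents support neither. What remains uncorrected is the estimate in the one trial actually run, given whatever imbalance is observed.

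A reader might also infer that precision is certainly lost. The gain depends on sample size and prognostic strength, and the documents give neither. With weak covariates, or about 30 patients in total, adjustment gains nothing or costs a little. This also stands, which is why the loss is only probable.

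Two practical objections stand as well. Item 3 lists a first lactate but gives no clock time and does not guarantee a value for every patient; it should not be read as a complete pre-insertion measurement. And the withdrawal criteria foresee death before insertion. A patient who dies before sampling has no lactate, and a complete-case model would drop that death from the primary outcome. Adjustment without a rule for missing values could therefore do harm.

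The opening reference in the Analysis Method section to an appropriate statistical test leaves room for a model but commits to none. Use of a t test for a binary outcome is a separate fault in the same sentence and adds no weight here; in the simulations the t test and chi-square rejected equally often.

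**Conclusion.** The point holds as a recommendation on efficiency and pre-specification. The plan's mortality comparison ignores two baseline variables that it already collects; it is valid, but probably less precise than it could be.

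Under assumed mortality of 61% v 35% and 30 to 50 per arm, the benefit is about 8-15% lower variance and 2-5 power points if the lactate odds ratio per SD is 2.0-2.5 (age 1.5). The power gain is about nil if both are 1.5. The downside is about 3 power points if neither is prognostic, and little or no gain in a very small trial. That these facts are in the text is certain; the size is not, because it rests wholly on assumed rates, numbers and covariate strength. The precision gain belongs to the standardised risk difference. A logistic odds ratio is conditional on the covariates, and its standard error need not be smaller.

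**What to change.** Rewrite the mortality part of the Analysis Method section to state:

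- **Primary analysis:** a covariate-adjusted comparison of in-hospital death in all randomised patients, by randomised group, with age and log first lactate (both continuous) as the only covariates, named before data are seen.
- **Effect measure:** the standardised (marginal) risk difference with 95% CI as primary; the conditional odds ratio as secondary.
- **Which lactate:** the item 3 sample only, taken before balloon pump insertion in Group B, and the matching first sample in Group A. Never the 6-hour repeat, which is post-treatment.
- **Missing lactate:** keep every patient, including early deaths, by simple imputation that ignores group and outcome, for example the overall median with a missing indicator. Say in advance what happens if the indicator predicts death perfectly, since a logistic fit would then break down.
- **Supportive analysis:** the unadjusted chi-square, not a t test.

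The cost is a paragraph or two of wording, with no new patients, procedures or measurements. The sponsor should confirm that SPSS 20.0, or another named program, gives the standardised risk difference with its interval; this has not been checked. A linear model with robust standard errors, as used in the simulations, estimates the risk difference directly.

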### **Treatment Duration**

During hospitalization

### **Primary Outcome**

In-hospital mortality
